4.4 Participant withdrawal from the study

This is not a treatment study and participants are free to withdraw at any time without consequences. The reason for withdrawal will be documented for all participants withdrawn from the study.

4.5 Recruitment / Enrollment Procedures

Participants will be recruited via word-of-mouth, internet, email, printed and/or broadcast CCHMC-approved advertisements in the community as well as contact from the volunteer database of the Clinical Trials Office. Recruitment will be continuous through the course of the study. If necessary to obtain adequate minority representation, under-represented racial groups might be targeted specifically for recruitment. Potential participants will undergo telephone screening to ensure that they meet the inclusion/exclusion criteria. If potential participants choose not to enroll or fail to meet inclusion criteria, all PHI will be destroyed.

Potential participants from the outpatient and inpatient clinics will be approached during the planning of their treatment at CCHMC by their clinical provider. If the patients express interest for the study, experimenters will contact them to confirm interest and assess eligibility.

4.6 Safety assessment and monitoring

This study involves no increase over minimal risk. Therefore, no data safety monitoring board will be created.

Any adverse event will be documented and reported to the Institution Review Board as soon as they are known. In addition, annual report of adverse events will be submitted in the annual review of the protocol.

5 Statistics

5.1 Statistical plan

5.1.1 *Analyses of neuroimaging data*

All structural and functional image data will be primarily processed by the FSL software package (FMRIB Software Library, Oxford, UK). Such processing will generally include motion correction, co-registration of structural and functional data, transformation of structural data to standard space, temporal and spatial filtering, image segmentation, and tractography. Other packages such as CONN, SPM, AFNI, FreeSurfer, and others may be used to augment image processing. Functional and structural data will be statistically analyzed using both parametric and non-parametric approaches, independent component analyses, in addition to multivariate pattern analysis. In general, fixed effects statistical models will be used for within-participants components of analyses, while random effects models will be used for between participant's components. These statistical analyses will generally be executed within FSL or similar software packages developed or adapted for analyses of functional and structural data.

5.1.2 Analyses of behavioral and psychophysical data

Questionnaires data will be scored and used to characterize patients-control differences and serve as potential covariates in current and future analyses.

The effect of behavioral factors on the trajectory of our outcome measures, i.e. changes in pain ratings, in functional disabilities over time, and brain function and structure, might be assessed by multilevel regressions and mixed ANOVAs. Post-hoc analyses will be performed when appropriate.

5.2 Number of participants to be enrolled

A total of 63 participants, i.e. 21 participants per group, will be enrolled in this study. Power calculations were performed for both imaging data and behavioral data to ensure an adequate sample size to detect changes in brain activity and interpret them in the context of behavioral effects.

Neuroimaging

Power calculations for neuroimaging data are challenging since such calculations depend crucially on effect size as well as properties of the imaging data and statistical approach used to deal with the multiple comparisons of >20,000 voxels. As no data is accessible so far in youth with CRPS, we used the NeuroPower tool to calculate statistical power and sample sizes based on our preliminary ASL data in youth with migraine, which study had a similar design to the one described here. Within-subject power calculations of ASL activation differences indicate that 19 participants per group would be required for 80% power with this imaging modality for treatment related changes in activity within group. All comparisons were calculated using z-transformed statistical images of the whole brain, a cluster-forming threshold of $z > 3.1$ and $p < 0.05$, isotropic smoothness of 5mm (8mm for ASL), and voxel sizes of 2x2x2mm, and a Gaussian Random Field theory-based approach for multiple comparisons. For these complex data, statistical power is defined as an 80% probability of correctly detecting an active peak for all peaks above the cluster-forming threshold.

Behavioral and psychophysical sample size estimation

We used G*Power to perform a power analysis for our behavioral data. This calculation resulted in an overall number of participants of 54, i.e. 18 participants per group, to achieve a small effect size f of 0.25 (Cohen, 1988) with a type I and II errors at 5%. An additional 15% has been added to that result to account for incomplete dataset due to participants' withdrawal and equipment failure. This number is consistent with that proposed for fMRI.

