Each testing session will include self-reported questionnaires for the children and their parents and a brain imaging session for the children. Each session will last approximately three hours for the children and 1.5 hour for the parents. Additional sessions might be scheduled in case of equipment failure.

To avoid distraction or psychosocial influences, participants to these studies will be alone with the experimenter during the sessions, with the exception of the consenting/assenting part of the study and the completion of the medical history and MRI screening forms. Similarly, parents will be left alone in a room while completing questionnaires. In addition, participants and their parents will be asked to shut down their cellphones and other electronic devices during the sessions to further avoid distraction.

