3.4.5 Brain imaging

3.4.5.1 Total scanning time

Together with inter-scan intervals and time needed for positioning participants in the scanner, the proposed sequences (below) can be obtained in a 1-1.5 hours duration MRI scanning session. This duration has been used in the vast majority of our imaging studies since 1992 and we have found that participants can tolerate this duration with minimal difficulty. Participants are queried for possible discomfort at the end of every series. Participants can generally remain still during the 5-12 minutes acquisition series and can shift/reposition arms and legs between series if needed. In case of an unexpected delay in the testing schedule scans will be run based on their importance to complete the study's aims. Their priority order is as follow: structural scan, resting-state Blood Oxygenation Level Dependent (BOLD), BOLD with sensory task, resting-state pCASL, and Diffusion tensor images (DTI).

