3.4.5.5 Cerebral Blood Flow (CBF)

This technique, which is regularly used in our laboratory, allows investigating relationships between brain activity and other variables. CBF may be measured in a fully quantitative fashion with pCASL imaging (Luh et al., 1999).

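### The 15% loss allowance in section 5.2 covers only the behavioural sample size; at that rate 21 per group leaves about 18 usable scans, one short of the 19 required for imaging

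*Combined protocol and SAP*

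**What the plan says.** Section 5.2 gives two sample size calculations and one enrolment figure.

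- **Imaging.** The calculation is "based on our preliminary ASL data in youth with migraine", run in NeuroPower. It concludes that "19 participants per group would be required for 80% power with this imaging modality for treatment related changes in activity within group".
- **Behavioural.** A G*Power calculation gives 54 in total, 18 per group, for f = 0.25 with both error rates at 5%.
- **Allowance.** Directly after the behavioural result: "An additional 15% has been added to that result to account for incomplete dataset". The causes named are participant withdrawal and equipment failure.
- **Enrolment.** "A total of 63 participants, i.e. 21 participants per group, will be enrolled in this study".
- **Link between the two.** The section closes with "This number is consistent with that proposed for fMRI".

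Other sections bear on how many ASL scans will be usable. Section 3.1 says "Additional sessions might be scheduled in case of equipment failure". Section 3.2.2 lets participants who do not attend in person give questionnaires and pain ratings remotely, which yields no scan. Section 3.4.5.1 places resting-state pCASL fourth of five scans if the schedule is unexpectedly delayed, and section 3.4.5.5 says "CBF may be measured in a fully quantitative fashion with pCASL imaging". Section 5.4 restricts analyses to data that pass quality assurance, and keeps partial datasets where the scan for a given condition was completed.

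**The concern.** The larger of the two requirements, 19 per group, has no stated allowance for loss. The smaller, 18 per group, has one. The closing sentence then calls the numbers consistent, and if the number it refers to is the enrolled 21, it sets an inflated figure beside an uninflated one.

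Because the 15% and that sentence stand next to each other, a reader can easily take 80% imaging power as holding after the planned loss. This matters because brain change is a named outcome (section 2.4.3) and part of Specific aim 3, and because section 5.2 presents its calculations as ensuring that changes in brain activity can be detected.

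**Working it through.** **Inputs, all from section 5.2:** imaging requirement 19 per group at 80% power; behavioural requirement 18 per group (54 in total); allowance 15%; enrolment 21 per group (63 in total).

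**1. Reproduce the enrolment figure.** 54 x 1.15 = 62.1, and 18 x 1.15 = 20.7, which rounds up to 21 per group and 63 in total. This matches. Dividing instead gives 18/0.85 = 21.2, so 22 per group. The plan therefore multiplied the requirement by 1.15.

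**2. Margin over the imaging requirement.** 21 - 19 = 2 per group. Measured on the same scale as the allowance:

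| Scale | Margin | Plan's allowance |
|---|---|---|
| Add-on to the requirement | 2/19 = 10.5% | 15% |
| Loss from those enrolled | 2/21 = 9.5% | 1 - 1/1.15 = 13.0% (15% if read as a loss) |

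The margin is short on both scales.

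**3. Usable participants per group at the plan's rate.** As an add-on, 21/1.15 = 18.3. As a loss, 21 x 0.85 = 17.85. Either way about 18, below 19.

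**4. Enrolment that would cover the same loss.** By the plan's own method, 19 x 1.15 = 21.85, so 22 per group. By division, 19/0.85 = 22.4, so 23 per group.

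**5. Approximate size in power.** The NeuroPower inputs are not in the documents, so the 19 cannot be re-derived and is taken as stated. As a proxy, take a one-sample t-test on within-person change and choose the standardised effect d so that power is 0.80 at n = 19. Power at other n is the upper tail of the noncentral t distribution with n - 1 degrees of freedom and noncentrality d x sqrt(n), beyond the critical value. Two thresholds give a range:

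| Usable n per group | Two-sided 0.05 (d = 0.680) | One-sided, equivalent to z > 3.1 (d = 1.045) |
|---|---|---|
| 21 | 0.842 | 0.865 |
| 19 | 0.800 | 0.800 |
| 18 | 0.776 | 0.759 |
| 17 | 0.749 | 0.713 |

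Averaging the same power over independent losses from 21 gives 0.764-0.779 at 13.0% loss and 0.745-0.769 at 15% loss. This is not the peak-wise power that section 5.2 defines, so it shows only the order of magnitude. Steps 1 to 4 do not depend on it.

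**The case against.** **The 15% is not an imaging rate.** This is fair: it is attached to the behavioural result, and no imaging loss rate is given. Applying it to scans is an inference. It is a reasonable one, because withdrawal and equipment failure remove scans as well as questionnaires, and no lower rate is offered for imaging.

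**Loss could be lower.** Extra sessions may be scheduled after equipment failure, and partial datasets are used. Both help, but a within-group change needs a usable ASL scan at both sessions compared. Keeping a partial dataset does not supply a missing scan, and a repeat session after equipment failure does not bring back someone who has withdrawn.

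**Loss could be higher.** A reader might infer from remote follow-up, quality exclusions and the low priority of pCASL that ASL loss must exceed 15%. The documents do not support a figure. The scan order applies only if there is an unexpected delay, and no rate is given for any of these causes. The low priority and the permissive wording on pCASL also suggest that ASL is not the leading scan, which lessens the consequence of a small shortfall.

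**The closing sentence is loose rather than false.** It may compare 18 with 19, or 21 with 19, and nowhere does the text say outright that 80% power remains after loss. That stands. The fault is an allowance left unstated for the larger requirement, beside wording that invites the wrong conclusion.

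**The effect is minor beside other uncertainty.** This also stands. Section 5.2 itself calls imaging power calculations challenging and takes its 19 from youth with migraine.

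**Conclusion.** The point holds, and it is small. At the plan's own loss rate, 21 per group leaves about 18, one below the 19 that section 5.2 requires, so the stated 80% imaging power does not survive that loss. This rests on two assumptions: that the 15% applies to usable ASL scans, and that the 19 is right as stated. If no more than 2 per group are lost, the 80% stands.

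The count of about 18 is firm under either reading of 15%. The power cost, roughly 76-78% at n = 18, is only indicative.

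Two stronger readings are tempting. One sets a 9.5% margin directly against 15%; that mixes a share of enrolment with an add-on to the requirement and overstates the gap. The other concludes that the imaging part is seriously underpowered or that enrolment must rise; a gap of about one participant per group, in a study that section 3.1 describes as primarily mechanistic, does not support that.

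**What to change.** Enrol no more participants, and restate section 5.2. Replace the sentence "This number is consistent with that proposed for fMRI" with wording such as: *80% imaging power holds only if at least 19 of the 21 in each patient group have usable ASL scans at both sessions compared. At the 15% allowance about 18 per group remain, and imaging power is below 80%.* Add the power at n = 18 and n = 17 from a rerun of the sponsor's own NeuroPower calculation with its migraine ASL inputs.

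The cost is one or two sentences and one rerun at two sample sizes. No procedure changes for the children. The downside is that the stated imaging power becomes slightly less favourable.

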3.2 Study sessions

The study described in this protocol will include up to three sessions. Each session will include the same testing components. Only the timing of the sessions differs (Figure 1). The timing of the sessions will be scheduled following the normal duration of the inpatient or outpatient treatment. No intervention will be scheduled during the regular inpatient or outpatient treatment at the FIRST clinic or at the Pain Management Center. In addition, no alteration of the usual inpatient or outpatient treatment associated with this study will occur.

Figure 1. Timeline of sessions

3.2.1 *First session*

The first session will take place right before or as early as possible during the inpatient or outpatient treatment of children diagnosed with CRPS.

Demographic information and medical history of the children and their parents will be reviewed with participants and their parents. A urine sample may be collected from female participants to test for pregnancy if they are post-menarchal. A urine sample will also be collected from all participants to assess the usage of non-prescribed drugs/substances. Healthy participants with positive tests for opioids or other analgesics will be excluded. In addition, participants and their parents will complete questionnaires assessing their psychological wellbeing, responses to pain, and influence of their social environment. Current pain sensations will be assessed in patients with CRPS by recording ratings of pain intensity and unpleasantness on VAS. To assess the extent of their pain, participants will report affected body parts on a picture of themselves and fill in the Pain and Symptom Assessment Questionnaire.

Participants will then undergo a brain MRI scan, during which fMRI, DTI, pCASL, and/or anatomical images will be collected to assess brain changes underlying CRPS. While in the

scanner, scans will be performed during rest and during tasks, including quantitative sensory testing and a multisensory visuo-audio-motor task.

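### The single behavioural power figure in section 5.2 fits a three-group interaction; for current pain, rated by patients only, power at f = 0.25 is nearer 91% than 95%, and f = 0.25 is conventionally medium, not small

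*Combined protocol and SAP*

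**What the plan says.** Section 5.2 describes the behavioural calculation in a few lines. The software is named ("We used G*Power to perform a power analysis for our behavioral data") and the result is given: "This calculation resulted in an overall number of participants of 54", that is, "18 participants per group, to achieve a small effect size f of 0.25". The error rates are set "with a type I and II errors at 5" per cent. For incomplete data, "An additional 15% has been added to that result", which leads to the enrolment target: "A total of 63 participants, i.e. 21 participants per group, will be enrolled in this study". The section does not state the test, the outcome, the number of repeated measurements, the correlation between them or a sphericity assumption.

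Section 5.1.2 lists the outcome measures whose trajectory is to be analysed: "changes in pain ratings, in functional disabilities over time, and brain function and structure". It says that multilevel regressions and mixed ANOVAs might be used.

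Section 3.2.1 says who rates current pain: "Current pain sensations will be assessed in patients with CRPS by recording ratings of pain intensity and unpleasantness on VAS". Section 3.2.2 again asks patients with CRPS for this at sessions two and three. Section 2.4.1 makes the pain-rating outcome wider, covering both spontaneous and experimental pain. The sensory testing battery in section 3.4.4, which includes visual analogue ratings of experimental pain, is described for participants in general.

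**The concern.** A reader of section 5.2 would take the behavioural outcomes as a whole to have 95% power for a small effect. Two features make that too favourable.

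First, the calculation appears to count all three groups, while one of the listed outcomes, change in current pain, has no control data. An analysis of that outcome rests on two groups and two thirds of the children.

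Second, f = 0.25 is called small. On the usual scale for f, 0.10 is small, 0.25 medium and 0.40 large. The documents do not print that scale, but it is standard.

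What is at stake is how a null result is read. If the trial finds no difference in pain trajectory, the text as it stands invites the conclusion that even small effects have been excluded with 95% power. The design does not support that.

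**Working it through.** **Inputs from the documents.** f = 0.25, alpha = 0.05, type II error = 0.05, 54 evaluable children in three groups of 18, 63 enrolled in three groups of 21, 15% added for incomplete data (all section 5.2); up to three sessions (section 3.2); mixed ANOVA as a candidate model (section 5.1.2); current pain rated by patients only (sections 3.2.1 and 3.2.2).

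**Inputs assumed.** Correlation between sessions rho = 0.5 and sphericity (epsilon = 1). Neither is stated in the documents.

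**Formula.** For a group-by-session interaction with k groups, m sessions and N children in total:

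- noncentrality: lambda = f² × N × m / (1 − rho)
- degrees of freedom: df1 = (k − 1)(m − 1), df2 = (N − k)(m − 1)
- power = probability that a noncentral F(df1, df2, lambda) exceeds the central 95% point

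**Step 1: reproduce the plan's figure.** k = 3, m = 3, N = 54:

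- lambda = 0.0625 × 54 × 3 / 0.5 = 20.25; df = 4 and 102; power = 0.958
- at N = 51, lambda = 19.125 and power = 0.946

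So 54 is the smallest balanced total that reaches 95%, which matches section 5.2. With this test, the reported 54 also points to a correlation near 0.5: rho = 0.4 would need 63 and rho = 0.6 would need 45. A total of 54 also arises for two measurements in one or two groups, but not as 18 in each of three groups. A time effect over two sessions in three groups just misses 95% at 54 (0.9499) and needs 57.

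The allowance for loss follows: 54 × 1.15 = 62.1, raised to 63 for equal groups.

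**Step 2: current pain, patients only.** k = 2, m = 3, everything else unchanged. The planned evaluable number is 2 × 18 = 36 and the enrolled number is 2 × 21 = 42.

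| Evaluable patients | lambda | df | Power at f = 0.25 |
|---|---|---|---|
| 36 | 0.0625 × 36 × 3 / 0.5 = 13.5 | 2, 68 | 0.906 |
| 42 | 15.75 | 2, 80 | 0.946 |
| 44 | 16.5 | 2, 84 | 0.956 |

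At 36 patients the type II error is 1 − 0.906 = 9.4%. The smallest balanced number reaching 95% is 44. A time effect across the two patient groups has the same degrees of freedom and noncentrality, so it gives the same 0.906 and 0.946.

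**Step 3: sensitivity at 36 patients.**

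| Setting | Power |
|---|---|
| rho = 0.3 | 0.78 |
| rho = 0.5 | 0.91 |
| rho = 0.6 | 0.96 |
| rho = 0.5, epsilon = 0.75 | 0.83 |
| rho = 0.5, two sessions only | 0.83 |

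**Step 4: what a conventionally small effect would mean.** k = 3, m = 3, N = 54, f = 0.10: lambda = 0.01 × 54 × 3 / 0.5 = 3.24, power = 0.25. Reaching 95% would take 312 children.

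**The case against.** The strongest reply is that section 5.2 contains no arithmetic error. The 54 is right for the three-group interaction, and the section never ties its 5% to pain ratings; it speaks of behavioural data in general. That stands. A reader might infer that the plan's stated type II error is wrong. The documents do not support this: it is right for the test that fits it, and what is missing is a separate figure for an outcome without controls.

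A reader might also infer that all pain ratings come from patients only. That goes too far. Section 3.4.3.1 mentions only patients, but sections 2.4.1 and 3.4.4 bring in experimental pain rated during sensory testing, and section 3.4.4 does not restrict that testing to patients. The point holds for current pain alone.

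A third reply is that the 91% is fragile. It rests on an inferred correlation and on the full planned loss. Current pain can be collected remotely at later sessions (section 3.2.2) and partial datasets are kept where possible (section 5.4), so loss on this outcome may be lower than 15%; with all 42 patients, power is 0.946. This also stands, and it is why both figures and the assumptions should be printed. Still, 36 is the plan's own evaluable number.

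Fourth, an inpatient-versus-outpatient comparison of pain trajectory is not a stated hypothesis: Aims 1 and 3 compare patients with healthy children, and Aim 2 relates baseline markers to recovery. That is fair, though the within-patient time effect gives the same power. Prediction from baseline markers is not powered by either calculation.

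Finally, 91% is ample and exceeds the 80% used for imaging in the same section. Agreed; this is a matter of accurate reporting, not of an inadequate sample.

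**Conclusion.** The point holds in a limited form. The one behavioural power figure in section 5.2 describes a three-group by three-session interaction. It does not carry over unchanged to current pain, for which power at f = 0.25 is about 91% with 36 evaluable patients: a type II error of about 9%, against the 5% stated for behavioural data in general. With no loss the gap nearly closes (about 95% at 42). These values assume three sessions, a correlation of 0.5 and sphericity, which reproduce the 54 but are not written in the plan.

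The label *small* is wrong by the usual convention whichever power settings are used. It does not change the sample size, but it changes what the plan appears to promise: for a conventionally small effect the three-group test has about one chance in four of detecting it.

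The sample size does not need to change.

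**What to change.** In section 5.2:

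- name the test behind the 54, the number of sessions, the correlation and the sphericity assumption;
- say that the 95% power applies to measures taken in all three groups;
- for current pain, which only patients rate, give about 91% at 36 evaluable patients and about 95% at 42, under the same settings, and make clear that this does not refer to experimental pain ratings from sensory testing;
- describe f = 0.25 as a medium effect.

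If the sponsor's G*Power run used other settings, those should be stated and the patient-only figures recalculated from them. The cost is a few sentences and a slightly less favourable stated power for one outcome. No extra children are needed.
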